6.9.3. Vital Signs, including Height and Weight

Vital signs will be summarized at Baseline and at Weeks 2, 4, 8, 12 and 16. Height will be reported at baseline only and weight will be summarized at baseline and Week 12.

6.9.4. Electrocardiogram

ECG parameters, if applicable, will be summarized at baseline.

6.9.5. Physical Examination

Physical examinations will be summarized at baseline and all-available post-baseline visits.

6.10. End of Study analysis

The Week 16 Analysis contains data up to and including Week 16. The definition of data cut for the analysis is detailed in [Appendix 2](#). The End of Study Analysis which contains additional data after the final database release, the two placebo sequences will not be combined. Data collected at Week 24 will be displayed in listings only, and will not be part of any analyses, unless specifically noted otherwise.

6.10.1. Weeks 18 and 20 Efficacy Endpoints

Only descriptive summaries will be provided.

6.10.2. End of Study Safety Summaries and Analyses

Selected subset of safety summaries will be produced.

7. INTERIM ANALYSES

This study uses an External Data Monitoring Committee (E-DMC). The E-DMC will be responsible for ongoing monitoring of the efficacy and safety of subjects in the study according to the charter. The recommendations made by the E-DMC to alter the conduct of the study will be forwarded to Pfizer for final decision. Pfizer will forward such decisions, which may include summaries of aggregate analyses of endpoint events and of safety data that are not endpoints, to regulatory authorities, as appropriate. Composition of the E-DMC and processes under which the E-DMC operates will be documented in the E-DMC charter.

9. APPENDICES

Appendix 1. Summary of Clinical Efficacy Analyses

Efficacy Endpoints	Population	Analysis Method	Missing Data Imputation	Primary Analysis for Co-primary Endpoints
Week 12 IGA Response	FAS	CMH	NR	Yes
Week 12 IGA Response	PPAS	CMH	NR	No
Week 12 IGA Response	FAS	CMH	TP	No
Week 12 EASI-75 Response	FAS	CMH	NR	Yes
Week 12 EASI-75 Response	PPAS	CMH	NR	No
Week 12 EASI-75 Response	FAS	CMH	TP	No
Week 2 NRS4 for severity Response	FAS	CMH	NR	
Week 16 IGA Response	FAS	CMH	NR	
Week 16 EASI-75 Response	FAS	CMH	NR	
Days 2-15, Weeks 4, 8, 12 and 16 NRS4 for Severity Response	FAS	CMH	NR	
Time to NRS4 for severity	FAS	Time to Event		
Weeks 2, 4 and 8 IGA Response	FAS	CMH	NR	
Weeks 2, 4, 8, 12 and 16 EASI-50, EASI-90, EASI-100 Response	FAS	CMH	NR	
Weeks 2, 4 and 8 EASI-75 Response	FAS	CMH	NR	
Weeks 2, 4, 8, 12 and 16 Percent CFBL in Total EASI Score	FAS	MMRM	OD	
Days 2-15, Weeks 2, 4, 8, 12 and 16 Percent CFBL in NRS for severity	FAS	MMRM	OD	
Weeks 2, 4, 8, 12 and 16 Percent CFBL in %BSA	FAS	MMRM	OD	
Weeks 2, 4, 8, 12 and 16 CFBL and Percent CFBL in SCORAD Total Score	FAS	MMRM	OD	
Weeks 2, 4, 8, 12 and 16 SCORAD50 Response	FAS	CMH	NR	
Weeks 2, 4, 8, 12 and 16 SCORAD75 Response	FAS	CMH	NR	
Weeks 2, 4, 8, 12 and 16 CFBL and Percent CFBL in SCORAD (VAS) for sleep loss	FAS	MMRM	OD	
CFBL=Change from baseline; CMH=Cochran-Mantel-Haenszel; ANCOVA=Analysis of Covariance; MMRM=Mixed-effect Model Repeated Measures; NR=Non-Responder; OD=Observed Data; TP=Tipping Point				

090177e1937d0b4e\Approved\Approved On: 18-May-2020 15:17 (GMT)

Appendix 2. Definition and Use of Data Cut and Visit Windows in Reporting

For both the Week 16 Analysis and End of Study Analysis, a data cut at Week 16 drug dispensing visit will apply to each subject before the windowing. Only data from up to and including the Data Cut will be used for the Week 16 Analysis. Only data from after the Data Cut will be used for the End of Study Analysis. If a subject withdrew from the study and no drug was dispensed at Week 16, all available data for that subject will be included in the Week 16 Analysis.

Week 16 Analysis:

Visit Label	Target Day	Definition [Day window]
Screening		Days -28 to Day -1
Baseline	Day 1, Baseline	Day 1
Week 2	15	Days 2 to 22
Week 4	29	Days 23 to 43
Week 8	57	Days 44 to 71
Week 12	85	Days 72 to 99
Week 16	113	Days 100 to 120

End of Study Analysis:

Visit Label	Target Day	Definition [Day window]
Week 18	127	Days 121 to 134
Week 20	141	Days 135 to 155
Follow Up/End of Study		
Week 24	-	Days 156 to -

Visit windows will be used for efficacy variables, and for any safety data that display or summarize by study visit. For other endpoints (eg, ECG, vital signs), visit windows will be applied for summary statistics by study visits if required.

For the lab values, if the calculated study day for the labelled baseline visit is not study Day 1 but falls within 28 days before the start of the study dosing, then that data should be used for the baseline instead of leaving baseline missing.

For the other values, if the calculated study day for the labelled baseline visit is not study Day 1, but falls before the start of the study dosing, then that data should be used for the baseline instead of leaving baseline missing.

Observations on the actual day will be used to analyze Days 2-15 Pruritus NRS. Weeks 2, 4, 8, 16 Pruritus NRS will be based on the windowing method.

If two or more visits fall into the same window, keep the one closest to the Target Day. If two visits are equaled distant from the Target Day in absolute value, the later visit should be used.

Safety analysis may follow CaPS.

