5.3.1. Binary Endpoints

For binary endpoints analyzed at each scheduled visit separately, visit windows (see [Appendix 2](#)) will be used to map all observed data into nominal visits. After mapping, for subjects who drop out for any reason, any data will be defined as “non-responsive” at all subsequent visits after the last observed value; for other subjects, any observations missing intermittently (including baseline values) will be considered missing completely at random (MCAR) and will remain missing in the analysis.

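### SAP Appendix 2 leaves a Week 16 dispensing visit on Day 121 or later in no usable window, so observed Week 16 IGA and EASI-75 results go unmapped

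*SAP*

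**What the plan says.** SAP Appendix 2 sets the order of operations: "a data cut at Week 16 drug dispensing visit will apply to each subject before the windowing". The data are then split in two. For the first part, "Only data from up to and including the Data Cut will be used for the Week 16 Analysis". For the second, "Only data from after the Data Cut will be used for the End of Study Analysis".

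Each analysis has its own window table. In the Week 16 Analysis table the last row is Week 16, target Day 113, "Days 100 to 120". In the End of Study table the first row is Week 18, target Day 127, "Days 121 to 134". The windows matter for the endpoints at issue: "Visit windows will be used for efficacy variables".

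There is one exception: "If a subject withdrew from the study and no drug was dispensed at Week 16, all available data for that subject will be included". It keeps these subjects' records in the earlier of the two analyses but adds no window beyond Day 120.

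SAP Section 5.3.1 says the windows are there to assign every observed record to a scheduled visit. It then gives two rules for values that are missing after that assignment. In subjects who drop out, visits after the last observed value count as non-response. In other subjects, intermittently missing observations "will be considered missing completely at random (MCAR) and will remain missing in the analysis". SAP Section 6 says the Week 16 Analysis runs through the date of the Week 16 visit itself.

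**The concern.** The cut already keeps every post-switch record out of the Week 16 Analysis, because it falls at the visit where the subject is reallocated (Protocol Section 6.2.7). The fixed Day 120 limit is not needed for that purpose. What it does is remove the visit label from a Week 16 assessment made on Day 121 or later. That record was observed on the randomised 16-week regimen, yet neither table can take it.

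IGA and EASI-75 response at Week 16 are key secondary endpoints inside the familywise error procedure (Protocol Section 9.2.2, SAP Section 5.1). A gap here means that an outcome that was seen is handled as if it had not been. It also leaves programmers to decide how to treat such records, possibly with treatment codes in hand.

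**Working it through.** **1. Apply the cut, then the windows.** Let c be the study day of a subject's Week 16 dispensing visit. A record on day d goes to the Week 16 Analysis if d ≤ c and to the End of Study Analysis if d > c. The assessment made at the dispensing visit has d = c, so it can only go to the Week 16 Analysis. There it is labelled Week 16 if 100 ≤ c ≤ 120.

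| Dispensing visit day c | Week 16 Analysis label | Eligible for End of Study (d > c)? |
|---|---|---|
| 110, 113, 116, 117, 120 | Week 16 | No |
| 121, 122, 125, 130 | none | No |

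By day number alone the two tables join without a gap (120, then 121). The gap appears only because the cut comes first.

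**2. The mirror case.** A record taken after the cut but on or before Day 120 (for example c = 110, d = 120) belongs to the End of Study Analysis, whose first window opens on Day 121. It too has no label.

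**3. Where Day 120 comes from, and how late other visits may be.** Day 120 is the midpoint of the Week 16 and Week 18 targets: (113 + 127)/2 = 120. Days of lateness accepted, as upper window limit minus target:

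- Week 2: 22 − 15 = 7
- Week 4: 43 − 29 = 14
- Week 8: 71 − 57 = 14
- Week 12: 99 − 85 = 14
- Week 16: 120 − 113 = 7

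A Week 12 visit 14 days late counts for the co-primary endpoints. A Week 16 visit 8 days late counts for nothing.

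**4. How far off schedule the affected visits are.** The protocol allows 113 ± 3, so at latest Day 116. The first affected day is 121 − 113 = 8 days after target and 121 − 116 = 5 days beyond the protocol limit.

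**5. Size.** First, the plan's own figure. For IGA response, 12% on placebo (n = 100) and 32% on active (n = 200), two-sided 5%, with power = Φ[(Δ − z·SE₀)/SE₁]:

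- pooled rate = (12 + 64)/300 = 0.2533
- SE₀ = √[0.2533 × 0.7467 × (1/100 + 1/200)] = 0.0533
- SE₁ = √[0.12 × 0.88/100 + 0.32 × 0.68/200] = 0.0463
- (0.20 − 1.96 × 0.0533)/0.0463 ≈ 2.06, so power is 98.05%

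This agrees with the stated minimum of 96%. The continuity-corrected form gives 97.2% and the unpooled form 99.1%.

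The documents give no count of visits after Day 120, so the loss is shown over an assumed proportion m, equal in all arms. The planned Week 12 rates stand in for Week 16, which is also an assumption. Both alpha levels at which the Week 16 sequence may be tested are shown.

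| m | Subjects of 700 | IGA power, 5% | IGA power, 2.5% |
|---|---|---|---|
| 0 | 0 | 98.05% | 95.9% |
| 1% | 7 | 97.95% | 95.7% |
| 2% | 14 | 97.8% | 95.5% |
| 5% | 35 | 97.5% | 94.9% |
| 10% | 70 | 96.7% | 93.6% |

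EASI-75 power stays at or above 99.6% throughout. The standard error grows by 1/√(1 − m): 1/√0.99 = 1.005 and 1/√0.97 = 1.015. At m = 1% to 3%, that is 200 × 0.01 = 2 to 200 × 0.03 = 6 subjects per active arm.

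**The case against.** The case for leaving a fixed limit is reasonable. These visits are already outside the protocol window, and bounding how late an assessment may be and still carry a visit label is ordinary practice. A window running to the cut with no ceiling would call a Day 150 visit Week 16. That matters most for dupilumab. Its last injection is planned for Week 14, target Day 99 (SAP Section 6.8.3.2), so an on-schedule subject is 14 days past it on Day 113, 22 days on Day 121 and 28 days on Day 127. The oral arms have no such planned stop, and estimating the difference between each dose and dupilumab at Week 16 is a stated objective. This stands, and it is why the fix needs an upper limit.

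It can also be said that the gap is a slip of wording. Sections 5.3.1 and 6 both point to keeping the record, and the SAP's version history says the windows were revised to close gaps. That is probably right about intent. But the tables are what gets programmed, and no sentence assigns the record to a visit.

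Several stronger readings are tempting and are not supported:

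- **Bias.** A reader might infer that late visits reflect illness or adverse events, so that the loss distorts the comparison. The documents say nothing on why visits run late or whether this differs by arm.
- **Certain treatment as MCAR.** The MCAR rule covers intermittent gaps, and Week 16 is the last visit of that analysis. If the subject counts as a dropout, the same section could instead make the value a non-response.
- **Loss of the subject.** Only the Week 16 value is lost. The subject stays in the Week 12 co-primary analyses and at earlier visits, and an assessment on Days 100 to 120 would still supply a Week 16 value.

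**Conclusion.** The concern holds as a defect in the window rules. Read as written, Appendix 2 gives a Week 16 dispensing visit on Day 121 or later no usable label. Observed results for two multiplicity-controlled key secondary endpoints then become missing, or possibly non-response, which contradicts Sections 5.3.1 and 6.

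The likely effect is small. At an assumed 1% to 3% of visits the standard error rises by about 0.5% to 1.5%. Even at 10%, IGA power at two-sided 5% is 96.7%, still above the planned minimum. The co-primary endpoints are unaffected, and nothing in the documents shows that a conclusion would change. The size rests on the assumed lateness rate, equal loss across arms, and Week 12 planning rates applied at Week 16. The gap itself rests only on the text of Appendix 2.

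**What to change.** Edit the window tables in SAP Appendix 2 before the Week 16 Analysis is unblinded:

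1. For subjects dispensed drug at Week 16, assign the assessment made at that visit, before the switch, to Week 16 up to a stated upper limit. Day 127 is one option: 113 + 14, the lateness already accepted at Weeks 4, 8 and 12. List any later visits.
2. Keep Day 120 as the limit for subjects with no Week 16 dispensing visit.
3. Give post-cut records on or before Day 120 a window in the End of Study table.
4. Report by arm how many Week 16 values were taken after Day 120, and add a sensitivity analysis that excludes them.

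The cost is a few lines of SAP text, one count table and one extra run of the Week 16 analyses. No post-switch data enter, because the cut still applies. The one real downside is that some off-schedule visits are admitted, including dupilumab subjects further from their Week 14 injection. Item 4 makes that visible.

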The investigator should assign the responsibility of unblinded administrator/trainer to a member of the study site staff who will not participate in any other study-related activities, ensuring that all other site staff do not risk becoming functionally unblinded. Contact between the unblinded administrator/trainer and study subjects should be kept to a minimum. The unblinded administrator/trainer must not take any action that may potentially reveal treatment assignment to the subject or site staff. The investigator, site staff, and any study participants other than the unblinded administrator/trainer must not be allowed to know the investigational product assigned to any study subject and must not be allowed to see the treatment records.

At Week 16, subjects previously receiving only placebo will receive PF-04965842 100 mg QD or 200 mg QD as per randomized allocation. Subjects previously receiving PF-04965842 100 mg QD or 200 mg QD will continue on this dose. Subjects previously receiving dupilumab will continue to take oral placebo. These alterations to study treatment will all be conducted while maintaining the blind, when re-issuing oral investigational product to all subjects at the Week 16 time point.

A guidance document with detailed dosing instructions will also be provided to subjects to support at-home dosing.

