6.2.7. Visit 8, Day 113/Week 16 (±3 days)

- Administer PROs including PtGA, DLQI, EQ-5D-5L, CCI HADS, and POEM;
- Obtain pre-dose vital signs including pulse rate, sitting blood pressure, respiratory rate and oral or tympanic temperature (after at least 5 minutes of rest);
- Review PSAAD daily completion (in selected countries), Pruritus NRS completion for this visit in the eDiary;
- Review any changes in the subject's concomitant medication and treatments information;
- Check subject understanding of protocol guidance for the use of background topical therapy as described in Section 5.9.1, ensure subject adherence to background topical therapy requirements and re-educate as required;
- Conduct targeted physical examination;
- Conduct clinical evaluations including IGA, SCORAD, EASI and BSA (calculated in the EASI);
- Perform a single 12-lead electrocardiogram (ECG);
- Obtain samples for laboratory testing: serum chemistry, hematology (including coagulation panel), lipid profile (fasting), and urinalysis;
- Urine pregnancy test (female subjects of childbearing potential). A negative urine pregnancy test must be obtained prior to dosing with the investigational product;
- Assess need for contraception and adherence to applicable lifestyle requirements (Section 4.4). Establish willingness and ability to comply with lifestyle requirements going forward in the study;
- Review eDiary to assess completion;
- Perform drug accountability procedures;

- Reallocate subject to new treatment regimen;
- Dispense oral investigational product to the subject;
- Administer oral investigational product and observe dosing;
- Assess and record any Adverse Events since the last visit.

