6. ANALYSES AND SUMMARIES

Unless specifically noted otherwise, the analyses specified in [Section 6](#) will be included in the Week 16 Analysis. The Week 16 Analysis contains data up to and including Week 16 Visit Date. The definition of data cut for the analysis is detailed in [Appendix 2](#). For all endpoints, comparisons will be done pairwise between each active treatment group (PF-04965842 200 mg QD, PF-04965842 100 mg QD and dupilumab) and placebo (three separate tests of hypotheses). For the Week 16 Analysis, the two placebo sequences will be combined into one group. Pairwise analyses with point estimates of the difference and the associated 95% confidence intervals will also be done among the active treatment groups

PF-04965842 200 mg QD, PF-04965842 100 mg QD and dupilumab. P-value will only be presented for the PF-04965842 doses vs. placebo (except for NRS4 at Week 2 and Days 2-15 where p-value for PF-04965842 doses vs. dupilumab will also be presented, see [Section 5.1](#)).

For the End of Study Analysis which contains additional data after the final database release, the two placebo sequences will not be combined.

A summary of analyses for clinical efficacy endpoints is provided in [Appendix 1](#). Visit windows to be used for all efficacy analyses and some relevant safety analyses are detailed in [Appendix 2](#).

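### The Week 16 data cut keeps the whole visit day, so an adverse event starting after a placebo subject's first PF-04965842 dose that day is tabulated as placebo and left out of the End of Study Analysis

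*SAP*

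**What the plan says.** **The cut.** SAP Appendix 2 states that "a data cut at Week 16 drug dispensing visit will apply to each subject before the windowing". The two analyses take opposite sides of it: "Only data from up to and including the Data Cut will be used for the Week 16 Analysis", and "Only data from after the Data Cut will be used for the End of Study Analysis". SAP Section 6 expresses the cut as a date, not a time: "The Week 16 Analysis contains data up to and including Week 16 Visit Date".

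**The labels.** SAP Section 6 also says: "For the Week 16 Analysis, the two placebo sequences will be combined into one group". Sections 6 and 6.10 keep the two sequences separate only in the End of Study Analysis. By Section 5, the final study report rests on the Week 16 Analysis, and the End of Study results go into a supplemental report.

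**The switch.** Protocol 5.5 says: "At Week 16, subjects previously receiving only placebo will receive PF-04965842 100 mg QD or 200 mg QD as per randomized allocation". Protocol 6.2.7, the Week 16 visit, includes the steps "Reallocate subject to new treatment regimen", then dispensing of oral product, then "Administer oral investigational product and observe dosing". The introduction to Protocol Section 6 confirms that visit-day doses are taken in the clinic.

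**Nearby rules.** SAP 3.5.1 uses the time of day, where collected, to decide whether an event on the first dosing day is treatment-emergent. SAP 4.3 classifies subjects in the safety set by the treatment they actually received. Appendix 2 closes by permitting the safety analysis to follow the sponsor's CaPS reporting standard.

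**The concern.** The last day assigned to placebo is also the first day on active drug. The cut is a calendar date, so it cannot separate the hours before the first PF-04965842 dose from the hours after it.

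An acute reaction to that dose would appear in the final study report as an adverse event on placebo. It would also be missing from the only analysis that shows the placebo-to-active sequences on their own. Visit windows cannot restore it, because the cut is applied before windowing.

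What is at stake is the comparison of each PF-04965842 dose with placebo. SAP 5.2.6 and 6.9.1 report risk differences for Tier-1 and Tier-2 events, with p-values for Tier-1. Drug-caused events counted under placebo shrink those differences. A serious reaction to the first dose would stand in the placebo column.

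Onset on the same day is plausible on the protocol's own figures. Section 1.3 gives a median time to peak concentration of 0.50 to 0.77 hours after repeated dosing.

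**Working it through.** **Step 1. Number of subjects affected.** The sample size text in Protocol 9.1 and SAP 2.2 gives 700 subjects at 4:4:4:1:1, with 50 in each placebo sequence. The ratio sums to 14, so each sequence has 700 × 1/14 = 50 and the pooled placebo group has 50 + 50 = 100. The stated figures are reproduced. Only subjects who are dispensed drug at Week 16 can be affected, so 100 is a ceiling.

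**Step 2. Follow one event.** A placebo subject attends at Week 16, takes the first PF-04965842 dose at the site, and has an adverse event start two hours later.

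- Week 16 Analysis: the onset date equals the visit date, so the event is included. The group label is pooled placebo.
- End of Study Analysis: the onset date is not after the cut, so the event is excluded.
- SAP 3.5.1: the event is treatment-emergent either way. The time-of-day test there concerns the first study dose, which was 16 weeks earlier.
- SAP 4.3: it classifies the subject and states no split by period for someone who received placebo and then active drug.

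**Step 3. Size per subject.** SAP 5.2.6 counts subjects, not events.

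- Pooled placebo incidence rises by at most 1/100 = 1.0 percentage point per newly counted subject.
- A 50-subject sequence loses at most 1/50 = 2.0 points per subject.

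These are maxima, because a subject who already had that event in the first 16 weeks is not counted again.

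**Step 4. Illustration over an assumed range.** Let q be the proportion of switching placebo subjects with a same-day event after the dose. The documents give no value for q. The expected number misplaced is 100 × q in pooled placebo and 50 × q per sequence. SAP 3.5.1 makes a preferred term Tier-2 when at least 4 subjects in any group have it. If every misplaced event had the same preferred term, the chance of reaching that threshold through misplaced subjects alone is P(X ≥ 4) with X ~ Binomial(100, q).

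| q (assumed) | Expected misplaced, of 100 | Expected lost per sequence of 50 | P(X ≥ 4) |
|---|---|---|---|
| 1% | 1 | 0.5 | 1.8% |
| 2% | 2 | 1 | 14% |
| 5% | 5 | 2.5 | 74% |
| 10% | 10 | 5 | 99% |

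Pooled placebo incidence rises by up to q, and each PF-04965842 minus placebo risk difference falls by up to q.

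**Step 5. Other data at the visit.** Protocol 7.10 puts patient-reported outcomes before product administration. Protocol 6.2.7 specifies pre-dose vital signs and lists the clinical evaluations ahead of dosing. No co-primary or key secondary result, and no alpha or power figure, depends on this rule.

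**The case against.** **The CaPS standard may already cover it.** The SAP ties safety endpoints and outputs to CaPS in several sections, and that standard may contain a rule for attributing events to treatment periods. This stands in part. One cannot say that no rule exists anywhere, only that the SAP states none. The closing line of Appendix 2 is permissive, however, and the content of CaPS is not in the documents. As written, the explicit rule is the inclusive cut.

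**The size is easily overstated.** A reader might infer that every misplaced event adds a full percentage point to placebo. It does not, because incidence counts subjects and many will already have had an event. A reader might also infer that the bias always favours PF-04965842. That direction applies only to events caused by the drug. Background events also occur on the visit day, and they carry no such direction. Nor do the documents give evidence that more than a handful of subjects, or any, would be affected. The window is part of one day out of about 113.

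**List order proves little.** Protocol 6.2.7 lists the adverse event assessment after dosing, but it does not say that its steps are in time order, and that assessment covers everything since the last visit. The argument here does not rely on it. It relies on the onset date and on the dose being taken at the visit.

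**Individual cases remain traceable.** Subject listings are planned (SAP 6.9) and causality is recorded for every event (Protocol 8.1.5). That would help with a single serious case, but it does not correct the tabulated risk differences.

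**A cut moved for placebo alone would bias the other way.** This is right, and it shapes the fix. Start times are used only if collected. Moving untimed visit-day events out of placebo but not out of the other arms would give placebo less capture time.

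**Conclusion.** The point holds within narrow limits. Appendix 2 and Section 6 together state a rule that assigns adverse events after the first active dose to pooled placebo for one part-day, and drops them from the End of Study Analysis. That is more than missing detail, because applying the rule as written produces the error.

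The size is at most 100 planned subjects, with at most 1.0 point of pooled placebo incidence and at most 2 points of a sequence's incidence per newly counted subject. The total depends on a same-day rate that the documents do not give. Drug-caused events misplaced in this way make PF-04965842 look safer relative to placebo.

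The conclusion rests on two assumptions: that the dose observed at Week 16 comes from the newly issued supply, which is the natural reading of Protocol 5.5 and 6.2.7 together, and that CaPS does not override the cut.

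A reader might infer that the Week 16 efficacy comparison is also contaminated. The documents do not support that, since the assessments that matter are placed before dosing. The issue merits correction because the final study report relies on these tables and the repair is cheap. It does not threaten the trial's main conclusions.

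**What to change.** In SAP Appendix 2, add a rule for adverse events that applies to all arms alike:

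- The cut is the first oral dose from the Week 16 supply, not the visit date.
- An adverse event starting on that date goes to the Week 16 Analysis if its recorded start time is before that dose.
- If it starts after the dose, or has no recorded time, it goes to the End of Study Analysis under the treatment then being taken. This matches how SAP 3.5.1 treats Day 1.
- Other Week 16 visit data collected before dosing stay in the Week 16 Analysis. The existing provision for subjects with no Week 16 dispensing is unchanged.

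If CaPS already contains an equivalent rule, the SAP should say so and state that it overrides the inclusive cut for adverse events.

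The cost is a short addition to the text and one programming condition. The downside is that untimed events which in fact preceded the dose on that one day move to the End of Study Analysis, but they do so by the same rule in every arm. No dose, visit or clinical procedure changes.
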